1.3. Sample Size and Power

Results of this study will be pooled with the results of a separate study being conducted in subjects with rheumatic diseases (GLPG0634-CL-227 [MANTA-RAY]) with the same objectives. The total planned number of subjects in both studies combined will be up to approximately 250 subjects.

A sample size of approximately 100 evaluable subjects per group (ie, 100 subjects in the filgotinib 200 mg group and 100 subjects in the placebo group) is adequate for the purposes of estimating cumulative distribution curves and producing a 95% confidence interval (CI) width that is reasonably narrow for the proportion of subjects in each group who experience a $\geq 50\%$ decrease in sperm concentration compared to baseline. An evaluable subject is defined as a subject with 2 semen samples at both baseline and at Week 13 that are eligible for mean calculation for sperm concentration, with visit window assignment for the mean calculation based on the date of the first of 2 evaluable sample collections. This 200 subject sample size is suggested in FDA's guidance on testicular toxicity studies {[U. S. Department of Health and Human Services \(DHHS\) 2018](#)}. Assuming a 20% rate of non-evaluable subjects at Week 13, up to 250 subjects may be enrolled to obtain 200 evaluable subjects.

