3.2. Subject Grouping

For analyses based on the All Randomized and ITT Semen Analysis Sets, subjects will be grouped according to their randomized treatment. For all other analysis sets, subjects will be grouped according to the actual treatment received. The actual treatment received will differ from the randomized treatment only when the actual treatment differs from randomized treatment for the entire treatment duration of the study drug administration period.

The following subject groupings will be applied to the semen and hormone data according to the actual treatment received:

- For the double-blind treatment period, data from subjects who took double-blind treatment will be summarized by treatment group (ie, filgotinib 200 mg and placebo).
- Semen and hormone data collected after Week 13 will be summarized by treatment sequence (ie, double-blind filgotinib, double-blind filgotinib to open-label filgotinib, double-blind placebo, and double-blind placebo to open-label filgotinib) for subjects with baseline and ≥ 1 visit at/after Week 26. Analysis visit windows for the double-blind placebo to open-label filgotinib group will be windowed from the first dose date of open-label filgotinib and will be 13-weeks prior to those who remained on original treatment. All other treatment sequences will have analysis visit windows assigned based on days from first dose of double-blind study drug.

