6.2. Primary Analysis of Primary and Secondary Endpoints

The primary analysis will be an observed cases analysis at Week 13 while subjects are on double-blind study drug as described in FDA’s guidance for industry on testicular toxicity studies {U. S. Department of Health and Human Services (DHHS) 2018}.

The main estimators of a While on Treatment Strategy estimand will be utilized for the primary analysis of primary and secondary endpoints at Week 13:

BINARY ENDPOINT	WHILE ON-TREATMENT STRATEGY
Population	Semen Analysis Set (subjects with 2 evaluable semen samples collected at baseline and at the Week 13 analysis visit) as defined in Section 3.1.2 of this SAP.
Patient Level Outcome to be Measured	Binary outcome for a subject meeting a $\geq 50\%$ decrease from baseline in sperm concentration at Week 13. Outcome is determined based on the mean of 2 evaluable semen samples at a visit.
Measure of intervention effect and handling of intercurrent events	Measure of treatment effect assuming that the treatment effect prior to the intercurrent event of treatment early termination is of interest. Data included to last dose date double-blind drug + 7 days will be considered “while on-treatment” for those who permanently discontinue double-blind study drug.
Population level summary measure	Difference in a binary outcome, comparing those assigned to filgotinib versus those assigned to placebo.
Estimators	
Main estimator: A stratified Mantel-Haenszel test (stratification factor: sperm concentration [15 - 50 and > 50 M/mL]) will be used to estimate the difference in proportions (filgotinib – placebo) and corresponding 95% CI {Koch 1989}. Calculations are provided in Appendix 2.
 
Note: When performing the stratified Mantel-Haenszel test, the 15 - 25 and > 25 - 50 M/mL strata for sperm concentration will be combined (eg, 15 - 50 M/mL) due to the small number of subjects in the lowest stratum; disease type will not be included as a stratification factor due to the small number of subjects with CD; and no subjects in this study received MTX.

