The number and proportion of subjects with a $\geq 50\%$ decrease in sperm concentration at Week 26 (observed cases) will be presented by double-blind treatment group. The number of subjects who have a $\geq 50\%$ decrease in sperm concentration at any time up to Week 26 (to upper bound of analysis visit window) will be displayed to ensure that $\geq 50\%$ decreases from baseline in sperm concentration that fell outside of the analysis visit windows are accounted for.

CONTINUOUS ENDPOINTS	WHILE ON TREATMENT STRATEGY
Population	Semen Analysis Set (subjects with 2 evaluable semen samples collected at baseline and at the Week 13 analysis visit) as defined in Section 3.1.2 of this SAP.
Patient Level Outcome to be Measured	Change and Percentage Change from Baseline (continuous outcome) at Week 13. Outcome is determined based on the mean of 2 evaluable semen samples at a visit, and analysis visit windows are assigned based on first of 2 evaluable semen samples.
Measure of intervention effect and handling of intercurrent events	Measure of treatment effect assuming that the treatment effect prior to the intercurrent event of treatment early termination is of interest. Data included to last dose date double-blind drug + 7 days will be considered “while on-treatment” for those who permanently discontinue double-blind study drug.
Population level summary measure	Median Difference between treatment groups, comparing those assigned to filgotinib versus those assigned to placebo in the change and percentage change from baseline at Week 13 for a continuous outcome.
Estimators	
Main estimator: Quantile regression models will be used to estimate the median difference (filgotinib – placebo) in change and percentage change from baseline at Week 13, 95% CI for the sperm/semen parameter of interest. The CI=RANK option will be specified in PROC QUANTREG in SAS.
 
For sperm concentration (M/mL), the model will include: baseline sperm concentration (continuous).
 
For sperm total motility (%), percent normal morphology, total sperm count (M/ejaculate) and ejaculation volume (mL), the model will include: baseline value for parameter (continuous), and sperm concentration (15 – 50 M/mL, > 50 M/mL).

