6.6.3. Hormones

Similar analysis methods used to summarize continuous secondary semen parameters will be used to analyze hormones LH, FSH, inhibin B, and total testosterone. Baseline will be the last value prior to administration of any study drug.

For all continuous hormone parameters, 8-point summary statistics (n, mean, SD, median, Q1, Q3, minimum, and maximum) by double-blind treatment group will be provided for the value at the visit, change from baseline, and percentage change from baseline in hormone parameter at Weeks 4 and 13 (change and percentage change values will be calculated from double-blind baseline). A 95% distribution-free CI on the median change and percentage change from baseline in all hormone parameters will be constructed by treatment at Week 4 and Week 13 using the

CIPCTLDF option in PROC UNIVARIATE in SAS. Quantile regression will be used to estimate the difference (filgotinib minus placebo) in median change and percentage change from baseline in hormones at double-blind Weeks 4 and 13 and to construct a 95% CI. The model will adjust for the baseline value of the hormone parameter as a continuous variable, and sperm concentration (15 - 50 M/mL, and > 50 M/mL). Since no subjects took concurrent MTX, and very few CD subjects were enrolled, these stratification factors will not be included in the model. The CI=RANK option will be specified in PROC QUANTREG in SAS.

Shift tables from baseline to Week 4 and Week 13 will be summarized by double-blind treatment group for the Semen Analysis Set for LH, FSH, inhibin B, and total testosterone. The shift tables include shift analysis for hormone parameters below, within, and above the central laboratory defined normal range for each specific hormone at baseline to below, within and above the normal range at Week 4 and Week 13.

Treatment-Sequence Hormone Displays for Week 26/OL Week 13 and Extension Phase

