Descriptive statistics will be presented at Baseline, Week 26/OL Week 13, and subsequent visits by actual treatment sequence to explore the confounding effects of response to treatment. Study days will be used for assignment of analysis visit windows for subjects who stayed on randomized drug throughout study and for subjects who started on double-blind filgotinib and switched to open-label filgotinib. For subjects who switched from placebo to open-label filgotinib, days on open-label filgotinib will be used to assign analysis visit windows at/after Open-Label Week 13. Week 26 for the first 3 treatment sequences will be displayed along-side OL Week 13 for placebo to OL filgotinib group; Week 39 alongside OL Week 26 for placebo to OL filgotinib group, etc. to align with the originally planned study weeks; but using the at/after Protocol Amendment 3 visit schedule to ensure that subjects were on open-label filgotinib for an entire sperm cycle for the placebo to open-label filgotinib group.

A summary of the 4 hormone parameters and change and percentage change from baseline by visit will be presented for subjects with evaluable semen data at both baseline and ≥ 1 of the analysis visits at/after Week 26/OL Week 13. Shift tables from baseline to Week 26/OL Week 13 for LH, FSH, inhibin B, and total testosterone will be summarized by treatment sequence for the Week 26/Extension Phase Semen Analysis Set.

A by-subject listing will be provided for hormones. A separate listing of the hormone data for subjects who entered the Monitoring Phase of the study will be provided.

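### SAP 6.6.3 limits the Week 4 and Week 13 hormone shift tables, and the hormone displays from Week 26/OL Week 13 on, to men with evaluable semen, and names no analysis set for the other Week 4/13 hormone analyses

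*SAP*

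**What the plan says.** For the early visits, SAP 6.6.3 says: "Shift tables from baseline to Week 4 and Week 13 will be summarized by double-blind treatment group for the Semen Analysis Set". SAP 6.2 describes the set as follows: "Semen Analysis Set (subjects with 2 evaluable semen samples collected at baseline and at the Week 13 analysis visit) as defined in Section 3.1.2". Section 3.1.2 itself was not in the text available here, so the definition is taken from this restatement.

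For Week 26/OL Week 13 and later, the summary of the four hormones "will be presented for subjects with evaluable semen data at both baseline" and at least one visit from Week 26/OL Week 13 on. The matching shift tables use the Week 26/Extension Phase Semen Analysis Set.

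For the Week 4 and Week 13 eight-point summaries, the distribution-free intervals on the median and the quantile regression, SAP 6.6.3 names no set. Two passages bear on it:

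- SAP 6.6.3 opens: "Similar analysis methods used to summarize continuous secondary semen parameters will be used to analyze hormones LH, FSH, inhibin B, and total testosterone". The stated population for those semen methods in SAP 6.2 is the Semen Analysis Set.
- SAP 3.2, on grouping semen and hormone data, says: "For the double-blind treatment period, data from subjects who took double-blind treatment will be summarized by treatment group". It sets no semen condition for that period.

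Protocol Appendix 2 schedules the hormone draws at Screening, Day 1, Weeks 4, 13 and 26, the open-label, LTE and Monitoring Phase visits, the 30-day follow-up and early termination. Protocol 8.2.1.2 makes the Semen Analysis Set primary for semen-related parameters and needs only one post-baseline semen sample. The protocol synopsis lists the sex hormones under safety evaluation, and Protocol 8.2.1.3 makes the Safety Analysis Set primary for safety endpoints.

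**The concern.** A hormone value does not need a semen sample to be valid. A man with baseline and Week 4 blood results who stops drug before the Week 13 semen window, or who stays on drug but gives only one usable Week 13 sample, drops out of the Week 4 shift table because of something that happened after the Week 4 draw. Selection on a post-randomisation event can differ by arm, so the tabulated groups need not be comparable in the way randomisation intended.

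This is a testicular-safety trial. Apart from early termination, no semen is scheduled between Screening and Week 13, so the Week 4 hormones are the only scheduled on-treatment gonadal measure in that interval. The men left out include those for whom semen evidence is thinnest. The supportive missing-data estimand in SAP 6.4 covers primary and secondary endpoints only; hormones are exploratory, so nothing there offsets the selection. SAP 6.7, which lists departures from the protocol for semen and hormone analyses, does not mention the choice of set.

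**Working it through.** **1. Order of the windows.** SAP Table 3-3 sets the hormone Week 4 window at Day 2 to 84 and the hormone Week 13 window at Day 85 to 112. SAP Table 3-4 sets the semen Week 13 window at Day 85 to 112. Because 84 < 85, every Week 4 shift-table entry depends on semen collected later.

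**2. Who is left out at Week 4.** Three kinds of men with a valid Week 4 value fail the Week 13 semen condition: those who stopped early, those still on drug with fewer than two evaluable samples, and those whose first sample falls outside Day 85 to 112. An early-termination draw before Day 85 and within 7 days of last dose also falls in the hormone Week 4 window.

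**3. Who is left out at Week 13.** The double-blind data cut is last dose + 7 days. A last dose before Day 78 (85 − 7) leaves no on-treatment Week 13 hormone value in any population. At Week 13 the semen rule therefore removes mainly men without an evaluable in-window pair.

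**4. The plan's own figure.** SAP 1.3: "Assuming a 20% rate of non-evaluable subjects at Week 13", 200 evaluable subjects need 200/(1 − 0.20) = 250. This reproduces the stated 250. The implied number failing the semen condition is 250 × 0.20 = 50, or 25 per arm at 1:1. SAP 1.3 gives 250 as the total for both studies combined, while SAP 1.2 gives up to 250 for this study, so 50 is an upper bound for this trial at that rate.

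**5. Precision at Week 4, if the restriction reaches the quantile regression.** Let f be the share of excluded men who have a Week 4 value. The documents do not give f, so a range is shown. With equal variance, the ratio of the restricted to the full-data interval width is √[(200 + 50f)/200] = √(1 + 0.25f). It depends on the 20% rate and on f, not on the total N.

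| f | Men omitted (50f) | Men available (200 + 50f) | Share of Week 4 values omitted | Width ratio |
|---|---|---|---|---|
| 0.25 | 12.5 | 212.5 | 5.9% | 1.031 |
| 0.50 | 25 | 225 | 11.1% | 1.061 |
| 0.75 | 37.5 | 237.5 | 15.8% | 1.090 |
| 1.00 | 50 | 250 | 20.0% | 1.118 |

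The shift tables are counts with no planned interval. For them only the omitted-men columns apply.

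**6. Bias, as illustration only.** Assumptions not in the documents: no true effect, a standard normal Week 4 change, 80% retained, and retention linked to that change in one arm only through a logistic model. By simulation, log-odds of 0.25, 0.5 and 1.0 per SD give false median differences of about 0.05, 0.09 and 0.16 SD. With no link the difference is zero.

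**The case against.** The strongest reply is that the explicit restriction covers less than it seems to. For the early visits, SAP 6.6.3 ties only the shift tables to the Semen Analysis Set. The Week 4 and Week 13 treatment comparison is the quantile regression, whose set is not named. Borrowing a method does not by itself import a population, SAP 3.2 speaks of men who took double-blind drug, and the note to Table 3-3 limits hormone data by dosing dates alone. This stands. A reader might infer that every hormone comparison is confined to men with semen pairs, but the text does not settle that. Equally, it does not rule it out, and two defensible readings of the population are themselves a gap.

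Other parts of the reply also stand:

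- The values are not discarded. SAP 6.6.3 provides a by-subject hormone listing, and SAP 3 says listings cover all randomized subjects.
- The exploratory hormone endpoint is defined at Weeks 13 and 26, not Week 4, and step 3 shows that early stoppers mostly have no Week 13 value to lose.
- Lack of response is a weak route to exclusion before Week 13. Response is judged at Week 13, and non-responders give two semen samples before switching. No difference in retention between arms is documented.

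A shared denominator for hormone and semen tables is a reasonable convenience when hormones help interpret semen findings. It justifies a supportive version. It does not justify making a Week 4 blood result depend on a Week 13 semen pair.

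**Conclusion.** The point holds for the displays where the restriction is written down: the Week 4 and Week 13 shift tables, and the hormone displays from Week 26/OL Week 13 on. At the planned 20% rate, the Week 4 shift tables could omit up to 50 of 250 men, and fewer if some of them have no Week 4 draw or if this study enrols only part of the 250. For the remaining Week 4/13 hormone analyses the fault is an unnamed set.

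A reader might infer a flat 12% loss of precision. The documents do not support that. The figure is the top of a 3% to 12% range, it needs every excluded man to have a Week 4 value, and it applies only if the quantile regression and median intervals are restricted too. A reader might also infer that a hormone signal would be hidden. The size and direction of any bias depend on how retention relates to hormone change in each arm, which the documents do not show.

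The conclusion rests on the restatement of the Semen Analysis Set in SAP 6.2. It concerns exploratory data and leaves the primary and secondary endpoints untouched. It is a worthwhile, inexpensive improvement rather than a threat to the trial's main result.

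**What to change.** In SAP 6.6.3, name the analysis set for each hormone display. Base the shift tables, eight-point summaries, median intervals, quantile regression and Week 26/OL Week 13 and later displays on all treated subjects with a baseline and an on-treatment hormone value in that visit window, whatever their semen status. Show the denominator at each visit. Keep the semen-set version as a supportive display.

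The cost is a wording change and one more population flag in programming; no new data are needed. The downside is that hormone and semen tables no longer share one denominator, which the supportive version covers. The SAP is signed, but SAP 1 provides for later changes to be documented in the clinical study report and SAP 2.5 plans a final analysis, so the change can be made there and labelled as made after SAP finalization.

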6.7. Changes to Protocol-Specified Analyses of Semen and Hormone Data

The protocol specified an analysis of covariance (ANCOVA) model adjusting for baseline value and stratification factors to estimate treatment differences (95% CI) for the continuous endpoints at timepoints where analysis was to be conducted for semen parameters and hormone data. Quantile regression was used in place of an ANCOVA model as medians were thought to be a more appropriate estimate than means for this data which is potentially skewed with outliers.

Since no subjects took concurrent MTX in this study, the subgroup analysis by MTX (yes, no) was not performed. MTX use (yes, no) and disease type were not included as stratification factors for the stratified Mantel-Haenszel test for the primary endpoint or as a dependent variable in quantile regression models for sperm/seminal parameters (secondary endpoints) or hormones (exploratory endpoints) since no subjects took MTX in this study, and only a few CD subjects were enrolled. The lowest 2 levels (15 - 25 M/mL and > 25 - 50 M/mL) for sperm concentration strata were combined in these analyses due to the small number of subjects in the lowest sperm concentration stratum.

7. ASSESSMENT OF RESPONDER/NON-RESPONDER AND DISEASE WORSENING

Composite scores including pMCS for UC and CDAI for CD will be listed using all the observed data based on the All Randomized Analysis Set.

7.1.1. Calculations of MCS and pMCS with the Subscores

The MCS is an instrument designed to measure disease activity in ulcerative colitis (Table 7-1). The MCS system is a composite index of 4 disease activity variables. Each variable is scored individually on an integer scale of 0 to 3, inclusive, with higher scores indicating greater disease activity. The individual components of the MCS include stool frequency (SF), rectal bleeding (RB), endoscopic subscore, and the physician's global assessment (PGA). Individual components of the MCS are described in Table 7-1 and MCS is calculated as the sum of the 4 subscores, ranging from 0 to 12. A pMCS is calculated as the sum of the 3 subscores excluding the endoscopic subscore; pMCS ranges from 0 to 9.

Table 7-1. Mayo Clinic Score

Variables	Score			
	0	1	2	3
Endoscopic Findings	Normal or inactive	Mild disease	Moderate disease	Severe disease
Rectal Bleeding	None	Streaks of blood in stool less than half the time	Obvious blood in stool half or more than half of the time	Blood alone passes
Stool Frequency (per subject recall)	Normal number of daily stools for patient	1-2 stools per day more than normal	3-4 stools per day more than normal	≥ 5 stools per day more than normal
Physician Global Assessment	None	Mild disease	Moderate disease	Severe disease

A Responder for UC is defined as a subject who has a reduction of ≥ 2 in pMCS compared to baseline at the specified assessment timepoint. A Non-responder will be defined as a subject who does not fulfill the definition of responder at the specified assessment timepoint.

Disease Worsening for UC is defined by a pMCS after Week 13 consisting of:

- an increase of ≥ 3 points to at least 5 points from the Week 13 value on 2 consecutive visits, or
- an increase to 9 points from the Week 13 value on 2 consecutive visits, if the Week 13 value was > 6 points

7.1.2. Calculation of CDAI Scores

The CDAI system is a composite index of 8 disease activity variables with scores ranging from 0 to over 600 based upon a composite of symptoms (eg, abdominal pain), signs (the presence of abdominal mass and weight), laboratory values (eg, hematocrit), and physician assessment amongst others. The CDAI has 3 patient reported outcome components: liquid or very soft stool frequency, abdominal pain and general wellbeing.

The total CDAI score for a specific visit is based on a weighted sum (rounded to the nearest integer) of all 8 variables as specified in Table 7-2. The CDAI total score will be set to 0 in the case the calculation leads to a CDAI total score of < 0. Each component will be selected within the analysis window as defined in Section 3.7.3.

Table 7-2. Calculation of Total CDAI Score

Variable no.	Variable	Variable description	Multiplier
1	Liquid or very soft stool (per subject recall)	Daily stool count is summed for 7 days	2
2	Abdominal pain (per subject recall)	Sum of 7 days of daily ratings as 0 = none, 1 = mild, 2 = moderate, 3 = severe	5
3	General wellbeing (per subject recall)	Sum of 7 days of daily ratings as 0 = generally well, 1 = slightly below par, 2 = poor, 3 = very poor, 4 = terrible	7
4	Complications	Number of listed complications: - Arthritis or arthralgia - Erythema nodosum, pyoderma gangrenosum or aphthous stomatitis - Iritis or uveitis - Anal fissures or fistulae or abscess - Other fistula - Fever over 37.8 C [100 F] during past week	20 each
5	Use of anti-diarrheal	Use of diphenoxylate or loperamide or other opiate for diarrhea 0 = No, 1 = Yes	30
6	Abdominal mass	0 = none, 2 = questionable, 5 = definite	10
7	Hematocrit*	Males: 47 – Hct [%] Females: 42 – Hct [%] *Result must be greater than or equal to 0. If negative result enter 0	6 x difference
8	Weight [#]	Percentage deviation from standard weight is (1-[weight/standard weight])*100. [#] Limit of -10 (result must be ≥ - 10)	1
CDAI score			TOTAL

CDAI = Crohn's Disease Activity Index; Hct = hematocrit
 {Sandborn 2002}

There are 2 lookup tables (1 for males; 1 for females) that are used to determine the standard weight for each subject. Two centimeters should be added to the eCRF collected height to account for height being collected shoeless. The look up tables were generated by a chart that is commonly used for CD studies for the Filgotinib program. The lookup tables exist as SAS datasets in the following celbook area: \\gsasdata\biometrics\global\cel\celbooks\IBD_ST_WT\0.

A Responder for CD is defined as a subject who has a reduction of ≥ 100 points in total CDAI score compared to baseline at the specified assessment timepoint. A subject with a baseline total CDAI score of ≥ 220 to ≤ 250 will be considered to be a Responder if a CDAI score of < 150 is attained at the specified timepoint. A Non-responder will be defined as a subject who does not fulfill the definition of responder at the specified assessment timepoint.

Disease Worsening for subjects with CD is defined by a total CDAI score after Week 13 consisting of:

- a score ≥ 220 on 2 consecutive visits, and
- an increase of ≥ 100 points from the Week 13 value on 2 consecutive visits

